## 16.1.2 Supportive Subgroup Analyses of Primary Endpoint

### Analysis set(s):

• Supportive analyses of the primary endpoint will be based on the mITT and PP analysis sets.

### Clinical cure rate by subgroup:

Again, analyses will be based on responders, which will be defined as was done in section 16.1.1 of this SAP. If the End of Study Kato-Katz egg count is missing, it will be imputed using the LOCF approach. Subgroup analyses of Part 1 and Part 2 of the study will be performed separately, by the following subgroups:

- Age category
- Gender
- Severity of infection
- Trial site (if applicable, i.e. more than one site)

Descriptive statistics of cure rates for each subgroup, individually and all in combination (four-way), will be estimated for each cohort using PROC FREQ.

Subgroup analysis will be performed utilising logistic regression to model clinical cure, i.e. *response* on gender, age category, severity of infection, day of assessment (e.g., Day 14-21), dose, formulation (ODT or not) and active pharmaceutical ingredient (L-PZQ or not [i.e. rac-PZQ]). The analysis will be repeated and presented separately for planned dose (mg/kg) *vs.* actual dose with respect to body weight (mg/kg) and actual dose in mg. Definitions and reference levels of subgroups are described in section 10.2.1 of this SAP. The PROC LOGISTIC procedure in SAS will be used with appropriate DESCENDING (to model on *response*=1) and PARAM=REF

(dummy coding for parameter estimates) statements to determine odds ratio point estimates and corresponding 95% Wald CIs.

To compliment PROC LOGISTIC results, the diagnostic plots using Pearson residuals will be produced [PLOTS(ONLY LABEL)=(INFLUENCE)].

Cure rate, in terms of proportion of responders, will be summarised by cohort (and by infection severity), and listed by cohort and subject. Estimates of cure rate will be presented graphically in the form of a forest plots presenting means and 95% CIs, by subgroup and cohort. For logistic regression results, odds ratio point estimates of model parameters and corresponding 95% CIs will be presented for each parameter, by cohort. Dose-response curves will be presented for the different active pharmaceutical ingredients (rac-PZQ/L-PZQ), separated by severity of infection, as well as pooled (all infections). Dose response curves will be generated for planned dose (in mg/kg), actual dose with respect to weight (in mg/kg) and actual dose in mg. These summary tables will be followed by the respective diagnostic plots.

Results will be presented for each analysis set.

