## 6 Summary of Clinical Trial Features

## 6.1 Study design and sample size

This is a phase II study consisting of two parts (Part 1 and Part 2). Part 1 will be conducted in a single study site. Part 2 will only start once Part 1 is completed.

**Part 1** is an open-label, randomized, controlled, dose finding study with three formulations of PZQ (commercial rac-PZQ tablets, oral disintegrating tablets of rac-PZQ and L-PZQ) in children aged 2-6 years infected with *S. mansoni*. Subjects will be randomized to one of the following arms:

- C1: commercial rac-PZQ tablets (Biltricide®) at 20 mg/kg dose t.i.d. (three times a day)
- C2: commercial rac-PZQ tablets (Biltricide®) at 40 mg/kg single dose
- C3: rac-PZQ ODTs at 40 mg/kg single dose

- C4: rac-PZQ ODTs at 60 mg/kg single dose
- C5: L-PZQ ODTs at 30 mg/kg single dose
- C6: L-PZQ ODTs at 45 mg/kg single dose
- C7: L-PZQ ODTs at 60 mg/kg single dose

An SMC will be formed to evaluate the interim safety analysis, and will continue to monitor the safety data on a regular basis in both Part 1 and 2, including recommendations about additional monitoring measures that may be deemed necessary. The SMC will consist of internal Sponsor members and Coordinating Investigators. Details regarding SMC roles, responsibilities, activities, procedures to reduce potential bias and possible SMC recommendations will be provided in a separate SMC charter.

After 20 patients from each of the cohorts C1 to C6 are treated, the acute (24 hour) safety data of all groups will be summarized and evaluated by the SMC, to decide on inclusion of the 7th arm (C7). C7 will be included in the randomisation scheme only after SMC approval while randomisation for the other groups can continue to 40 subjects per arm.

Part 2 will run after all subjects in Part 1 (C1-C6/7) have completed and are reviewed by SMC.

A cohort with infants of 13-24 months infected with *S. mansoni* (C8) and a cohort with infants of 3-12 months infected with *S. mansoni* (C9) will be enrolled in an age-staggered approach.

Infants in cohort C8 will be treated with rac-PZQ or L-PZQ ODTs at the optimal dose level selected by SMC from Part 1 (based on benefits-risks evaluation). In addition, a maturation factor will also be included (if applicable) to decide on the dose for these infants.

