## 7 Sample Size/Randomisation

## 7.1 Sample Size

Part 1: this study is exploratory. There is no hypothesis testing.

The sample size is based on the minimum number of subjects to reach a meaningful precision of the primary efficacy endpoint estimate (cure rate) in each arm, considering the stratification factor.

There are limited historical data on the impact of the severity of infection on the observed cure rate. In the recent study by Keiser et al. (unpublished data), the observed cure rate in *S. mansoni* infected children varied between 55% and 60% in moderately infected children and 70% and 85% in light infected children depending on the dose. The table below presents the overall cure rate projections according to different assumptions of true cure rate in mild (low) and moderately infected children.

Overall cure rate (95%CI),	Assump	tions of Cure F	Rate in Light In	fections
(N=50)	70%	75%	80%	85%

	50%	62% (48%, 74%)	65% (52%, 78%)	68% (56%, 80%)	71% (60%, 82%)
Assumptions of	55%	64%	67%	70%	73%
Cure Rate in		(50%, 76%)	(54%, 80%)	(58%, 82%)	(62%, 84%)
Moderate/Heavy	60%	66%	69%	72%	75%
Infections		(52%, 78%)	(56%, 80%)	(60%, 84%)	(64%, 86%)
	65%	68% (54%, 80%)	71% (58%, 82%)	74% (62%, 86%)	77% (66%, 88%)

A minimum-clinical meaningful cure rate is considered as equal to 70%. With 50 evaluable patients enrolled, stratified as 40% moderate/heavy and 60% light, the corresponding 95% CI lower bound of an observed cure rate of 70% would be above ~58%, depending on potential difference between the strata. This sample size would also provide the minimum number of subjects to estimate the cure rate within strata.

Considering the efficacy criteria for the selection of the dose (observed cure rate >70%), through simulations, the table below presents the probability of observing an overall cure rate >= 70% based on different scenarios of true cure rates based on different strata, assuming a stratification of 40% moderate/heavy infections and 60% light infections.

Probability of observ	ring a	Assumptio	ns of Cure I	Rate in Ligh	t Infections
cure rate $\geq 70\%$ , N	=50,	70%	75%	80%	85%
	50%	15%	27%	45%	64%
Assumptions of Cure Rate in	55%	23%	38%	57%	76%
Moderate/Heavy Infections	60%	33%	51%	70%	85%
intections	65%	45%	63%	80%	92%

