## 7.2 Randomisation

Part 1: Treatment allocation will be random and balanced at a ratio of 1:1:1:1:1:1. Randomisation will be stratified by the infection severity (40% moderate/heavy and 60% light infections). After 20 subjects/arm are randomized, the SMC will decide on the inclusion of the 7th arm.

Randomisation will continue for arms C1-C6 at a ratio of 1:1:1:1:1:1 until 40 subjects/arm are randomized.

If the C7 arm is included, randomisation will continue with an allocation ratio of 1:1:1:1:1:1:3 until a total of 60 subjects/arm are randomized in the 7 arms. If C7 arm is not included, the allocation ratio will remain the same (1:1:1:1:1) until a total of 60 subjects/arm are randomized in the 6 arms, as shown below.

Randomisation lists indicating a randomisation number and which treatment is to be given, will be produced prior to the start of the trial by the statistician at the **PPD**...Based on the randomisation lists sequentially numbered sealed envelopes which contain a randomisation number and the treatment allocation will be prepared. The sealed randomisation envelopes will look identical and will be kept in a locked cupboard to which only the study

Part 2: There is no randomisation in this part.

pharmacist will have access.

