#### Significance level:

All statistical tests mentioned in this SAP are to be regarded as exploratory. All statistical tests comparing treatment arms will be performed two-sided. If confidence intervals are to be calculated, these will be two-sided with a confidence probability of 95%, unless otherwise specified in this SAP.

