### **Overall clinical cure rate:**

Subjects cured of infection during the trial will be labelled as "responders". Responders will be defined as subjects with no parasite eggs (as determined by Kato-Katz method) in the End of Study

stool samples, 14-21 days after treatment, according to the eCRF page "Follow-up visit on D14-D21". Responders and non-responders will be coded as follows:

- For responders, *response* = 1
- For non-responders, response = 0

If the End of Study Kato-Katz egg count is missing, it will be imputed using the Last Observation Carried Forward (LOCF) approach. Subjects with missing data will be considered non-responders.

The proportion of responders in each cohort will be determined based on a binomial distribution. Exact 95% CIs will be calculated based on the Clopper-Pearson method. The PROC FREQ procedure in SAS will be used with the appropriate BINOMIAL and EXACT statements for point estimates and corresponding 95% CIs.

Point estimates and corresponding 95% CIs will be presented for cure rate, in terms of proportion of responders, by cohort. Response will be listed by cohort and subject. Estimates of cure rate will be presented graphically in the form of forest plots presenting means and 95% CIs.

Results will be presented for each analysis set.

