#### Categorical data:

In terms of clinical cure, the Mantel-Haenszel Chi-Square trend test will be performed between planned dose (in mg/kg) and response frequency, for each treatment administered, i.e.:

- Biltiricide®
- rac-PZQ ODT
- L-PZQ ODT

Similar trend tests will also be applied to actual dose, where actual dose will be categorised as follows:

- Less than 30 mg/kg
- 30 40 mg/kg
- 40 50 mg/kg
- 50 60 mg/kg
- 60 70 mg/kg
- More than 70 mg/kg

Again, results will be grouped by:

- Biltiricide®
- rac-PZQ ODT
- L-PZQ ODT

Trend test results will be tabulated. In addition, forest plots of response against planned dose will be presented by treatment administered, as listed above.

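### If C7 opens, all of its children but only a third of each other arm are randomised last, and the dose-response model and L-PZQ trend test have no phase term

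*SAP*

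**What the plan says.** SAP 7.2 describes Part 1 allocation in steps. First: "Randomisation will continue for arms C1-C6 at a ratio of 1:1:1:1:1:1 until 40 subjects/arm are randomized". SAP 6.1 makes the seventh arm conditional: "C7 will be included in the randomisation scheme only after SMC approval". If it is approved, "randomisation will continue with an allocation ratio of 1:1:1:1:1:1:3 until a total of 60 subjects/arm are randomized in the 7 arms". Stratification is by infection severity only.

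Three outputs use the resulting data:

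- **Primary analysis (SAP 16.1.1).** "The proportion of responders in each cohort will be determined based on a binomial distribution", with exact confidence intervals and no hypothesis test.
- **Supportive logistic model (SAP 16.1.2).** Cure is regressed on age category, gender and "severity of infection, day of assessment (e.g., Day 14-21), dose, formulation (ODT or not) and active pharmaceutical ingredient (L-PZQ or not [i.e. rac-PZQ").
- **Dose trend (SAP 16.3.2).** "the Mantel-Haenszel Chi-Square trend test will be performed between planned dose (in mg/kg) and response frequency, for each treatment administered". For L-PZQ this covers C5, C6 and C7.

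The subgroup list in SAP 10.2.1 has no phase or enrolment-date entry. SAP 11 states: "All statistical tests mentioned in this SAP are to be regarded as exploratory". The Protocol synopsis plans Part 1 enrolment from June 2016 to December 2017, about 18 months.

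**The concern.** C7 is the highest L-PZQ dose and the only arm enrolled entirely in the last phase. If the cure rate moves during enrolment for reasons outside the model, C7 takes the whole change and every other arm a third of it. Part of the drift then looks like an effect of dose or ingredient at the top of the L-PZQ curve. A fall could hide a dose response and a rise could mimic one. Day of assessment does not help, because it records when within days 14-21 the stool was read.

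Severity needs a separate word. It is in the logistic model, but the trend test has no severity term. Stratified randomisation balances severity between arms within a phase. The documents do not say whether the planned 40:60 split is held separately in each phase. If it is not, a change in severity mix between phases could also reach the trend test.

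At stake is how the dose-response outputs are read when Part 1 results go to the safety committee for the Part 2 recommendation (SAP 8.2).

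**Working it through.** **Allocation, reproducing the plan's totals (SAP 7.2).** Early phase: 6 × 40 = 240. Late phase: 60 − 40 = 20 in each of C1-C6, and 3 × 20 = 60 in C7, so 120 + 60 = 180. Total 240 + 180 = 420, as planned. Late share: C7 60/60; every other arm 20/60.

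**Assumptions (not in the documents).** Early cure 75%, no effect of dose, formulation or ingredient, no missing data, and a change of 5 or 10 points between phases in either direction.

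**Shift in a simple contrast.** Bias in C7 minus another arm = drift × (1 − 20/60). For 5 points: 5 × 2/3 = 3.3. For 10 points: 10 × 2/3 = 6.7.

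**L-PZQ trend test.** Mantel-Haenszel trend over 30, 45 and 60 mg/kg, 60 children per arm, 200,000 simulations, two-sided 5% level:

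| Drift | Planned test | Stratified by phase |
|---|---|---|
| None | 5.0% | 5% |
| Fall of 5 | 7.0% | 5% |
| Rise of 5 | 6.8% | 5% |
| Fall of 10 | 12.6% | 5% |
| Rise of 10 | 14.3% | 5% |

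**Logistic model, dose linear.** This is a fit to expected counts in seven arms with dose, formulation and ingredient; C1 is taken as 60 mg/kg in total. SE is that of the log odds ratio.

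| Drift | Dose OR per 15 mg/kg (SE) | Ingredient OR (SE) |
|---|---|---|
| Fall of 10 | 0.92 (0.146) | 0.87 (0.264) |
| Fall of 5 | 0.96 (0.149) | 0.93 (0.270) |
| Rise of 5 | 1.05 (0.159) | 1.08 (0.286) |
| Rise of 10 | 1.11 (0.165) | 1.19 (0.297) |

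The log odds ratios at 10 points are −0.085 and +0.109 for dose, and −0.135 and +0.173 for ingredient. The largest ratio of shift to SE is 0.109/0.165 = 0.66. With a phase term both odds ratios return to 1.00. Adding severity (85% cure in light and 60% in moderate/heavy infection, mixed 60:40) barely changes the 10-point result: dose OR 0.91 or 1.13, ingredient OR 0.86 or 1.21.

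**Logistic model, dose categorical.** SAP 16.1.2 specifies reference-cell coding (PARAM=REF), so dose may be entered as categories. The 30 and 45 mg/kg levels then occur only in L-PZQ arms, so the ingredient term rests on C7 against the racemate arms, with C4 the ODT arm at the same dose. This can be done by hand:

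- Fall of 10: C7 65%, odds 0.65/0.35 = 1.857. C4 (40 × 75% + 20 × 65%)/60 = 71.67%, odds 2.529. Ingredient OR 1.857/2.529 = 0.73; log −0.309, SE 0.367.
- Rise of 10: C7 85%, odds 5.667. C4 78.33%, odds 3.615. Ingredient OR 1.57; log 0.449, SE 0.452.

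Both are under one SE, the second only just (0.449/0.452 = 0.99).

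**The case against.** The case against rests on four things.

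**Drift is undocumented.** A reader might infer from Protocol 3.6, which says areas can differ in susceptibility to treatment, that cure will drift as recruitment moves from village to village. The documents do not support that. The sentence explains why the reference arms are included; it does not describe differences within one recruitment region or over time. Protocol 7.1.1 lists all children before the study and informs all village households when it begins. That does not exclude staged recruitment, but nothing says that villages are enrolled in sequence. Part 1 has one site. This objection stands, so the point is conditional.

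**The primary analysis is not affected.** A reader might infer that C7 is more likely to miss the efficacy criterion, which SAP 7.1 describes as "Considering the efficacy criteria for the selection of the dose (observed cure rate >70"%). Each arm's rate is a plain description of the children in it, and a phase term does not change it. Any probability of passing 70% would also depend heavily on missing data. If one-sixth of an arm were missing and counted as not cured, a true 75% would give an expected 0.75 × 50/60 = 62.5%. Such probabilities should not be used to size this point.

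**Concurrent controls already exist.** C1-C6 contribute 120 late children, so phase could be examined after the fact, and SAP section 5 allows unplanned analyses if labelled. That is true, but an adjustment chosen after results are seen carries less weight than one fixed beforehand.

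**Everything affected is exploratory and small.** This also stands. No decision rule in the documents uses the model or the trend test, and the model shifts are under one SE. It limits the importance of the point but does not remove the gap.

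**Conclusion.** The gap is real and the consequence conditional. C7 must open, and cure must change between phases for reasons the model does not already cover. Two-thirds of any such change then enters C7 minus any other arm; that fraction follows from SAP 7.2 alone. The sizes in points, rejection rates and odds ratios rest on the assumptions listed, and the odds ratios also depend on how dose is coded. On those assumptions a 10-point drift raises false rejection by the L-PZQ trend test from 5% to 13-14%. The expected model shifts remain under one SE.

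The risk is a misread description of the top L-PZQ dose in exploratory outputs. The documents do not support a claim that the primary estimates are wrong, that the 70% criterion is undermined, or that a formal conclusion would fail. This is an improvement to consider.

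**What to change.** 1. **If C7 opens, add randomisation phase (before or after C7 opened) as a covariate in the SAP 16.1.2 model.** Phase is known from the randomisation list, so no new data are needed. With dose linear, the dose SE rises about 3-6% (0.146 to 0.151 at a 10-point fall; 0.165 to 0.175 at a 10-point rise). With dose categorical, the ingredient SE rises about 8-12%. The SAP should also state which coding of dose is meant.

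2. **Optionally, report a phase-stratified L-PZQ trend test beside the planned one in SAP 16.3.2, as a sensitivity analysis only.** Without drift it loses power: 39.8% to 32.5% for an OR of 1.5 per 15 mg/kg with C5 at 75%, and 75.4% to 64.7% for an OR of 2. With a 10-point fall applied as a constant log-odds shift it does better than the planned test (37.6% against 21.7%, and 73.5% against 63.7%).

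Comparing C7 only with concurrently randomised children is not a useful remedy. With 60 against 20 and 75% cure, the 95% half-width is 1.96 × √(0.75 × 0.25 × (1/60 + 1/20)) = 0.219. With full arms it is 0.155. An interval of ±22 points cannot separate a 6.7-point bias from chance.

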After 5 to 10 infants age 13 to 24 months have been enrolled, the overall safety and efficacy data in these patients will be evaluated by the SMC for the decision to include the lower age group of infants (cohort C9). SMC will also decide whether dose level adaptations are needed before starting enrolling C9.

Total number of subjects: 360-420 (if C7 is included) enrolled subjects in Part 1 and 40 enrolled subjects in Part 2.

Number of subjects per treatment arm:

Part 1: 60 enrolled subjects in each cohort (C1 to C7)

Part 2: 30 enrolled subjects in the 13-24 months cohort (C8)

10 enrolled subjects in the 3-12 months cohort (C9)

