### Clinical cure rate by POC-CCA:

CR by POC-CCA will be analysed in the same manner as CR by Kato-Katz as described above. In addition, estimates of cure rate will be presented graphically in the form of forest plots presenting means and 95% CIs of treatment groups and proportion of patients with each POC-CCA response (negative, positive 1+, positive 2+ and positive 3+) for the following time points:

- D-28 to D-1
- D2
- D8
- D14- D21

The proportion of CCA negative, 1+, 2+ and 3+ participants (colour-coded for category) will be plotted over time, for each of the cohorts. The same will be plotted for treatment types (Biltricide®, rac-PZQ and L-PZQ), instead of cohorts.

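### Part 2 logistic models: Wald intervals in about 40 infants, with no fallback if a covariate level is fully cured

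*SAP*

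**What the plan says.** SAP section 16.1.2 states: "Subgroup analyses of Part 1 and Part 2 of the study will be performed separately, by the following subgroups". It continues: "Subgroup analysis will be performed utilising logistic regression to model clinical cure". The covariates are gender, age category, severity, day of assessment, dose, formulation and active ingredient. The estimator is PROC LOGISTIC with no option that changes its default maximum likelihood, and the output is given as "dummy coding for parameter estimates) statements to determine odds ratio point estimates and corresponding 95% Wald CIs". An odds ratio and interval are promised for every parameter. Section 11 fixes the level of confidence intervals: "these will be two-sided with a confidence probability of 95" per cent.

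The Part 2 numbers are in SAP section 6.1: "Part 2: 30 enrolled subjects in the 13-24 months cohort (C8") and "10 enrolled subjects in the 3-12 months cohort (C9"). For the secondary endpoint, section 16.2.1 says "CR by POC-CCA will be analysed in the same manner as CR by Kato-Katz as described above".

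No penalised, exact or profile-likelihood option is named for the model, and there is no rule for separation or non-convergence. The EXACT statement in section 16.1.1 belongs to PROC FREQ and serves the Clopper-Pearson intervals for the cohort cure rates.

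**The concern.** A Wald interval needs a finite estimate with a roughly normal error. With 10 infants in one age group and an effective drug, a covariate level with no failures is a realistic outcome. The data then separate: the fitted log odds ratio grows with each iteration, its standard error grows faster, and the interval ends up covering everything. This happens even when the observed difference between the groups is large. The table of odds ratios would then hold an entry that carries no information on the contrast, and any replacement method would have to be chosen after the data were seen.

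**Working it through.** **Inputs.** C8 n = 30 and C9 n = 10 (SAP 6.1); 95% two-sided intervals (SAP 11); missing outcome counted as non-response (SAP 16.1.1). The documents give no cure rate or infection mix for infants. For orientation, protocol section 3.4.2.1 reports 75.0% for children overall at 40 mg/kg, 79.4% for the first age group in its Table 1, and 91.7% at ages 4-6 at 60 mg/kg (24 children). Applying any of these to infants is an assumption.

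**The plan's own figure.** There is none for Part 2 or for this model. The only stated operating characteristic is for Part 1: about 85% to observe at least 70% cure with N = 50. The exact sum of Binomial(20, 0.60) and Binomial(30, 0.85), P(X ≥ 35), gives 84.7%, so it reproduces.

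**Step 1: the failure.** In an age-only model, with x cured out of n in each group, the Wald interval is log OR ± 1.96 × SE, where SE² = 1/x₁ + 1/(n₁ − x₁) + 1/x₂ + 1/(n₂ − x₂). With C9 at 10/10 the last term is 1/0. Iterating the fit for C8 15/30 against C9 10/10:

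| Iterations | log OR | SE | z |
|---|---|---|---|
| 8 | 9.2 | 32 | 0.29 |
| 15 | 16.2 | 1,043 | 0.016 |
| 25 | 26.2 | 154,841 | 0.0002 |

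In this two-group case the Firth estimate equals adding 0.5 to each cell, so it stays finite. For the same data OR = (10.5/0.5)/(15.5/15.5) = 21, profile 95% CI 2.3 to 2,789, Fisher p = 0.006. In the other direction, C8 30/30 against C9 5/10, OR = (5.5/5.5)/(30.5/0.5) = 0.016, CI 0.0001 to 0.18, Fisher p = 0.0004.

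**Step 2: how often.** At a common true cure rate p, P(an age group is fully cured) = p¹⁰ + p³⁰ − p⁴⁰:

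| p | p¹⁰ | p³⁰ | P |
|---|---|---|---|
| 75% | 0.056 | 0.0002 | 6% |
| 79.4% | 0.100 | 0.001 | 10% |
| 85% | 0.197 | 0.008 | 20% |
| 90% | 0.349 | 0.042 | 38% |

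A fully uncured group adds a negligible amount at these rates. With age, sex, severity and day in the model (1,000 simulated data sets per scenario), separation occurs in 8%, 15% and 54% at 75%, 79.4% and 90% cure if 40% of infections are moderate/heavy, and in 41%, 48% and 81% if only 10% are. The 40% is the Part 1 stratification; the 10% is an assumed lower end.

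Missing data work the other way in mITT. With a fraction d missing, P(10/10 in C9) = (p(1 − d))¹⁰. At p = 90% this is 35% with none missing, 21% with 5% missing and 5% with 17% missing (17% is the Part 1 dropout assumption).

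**Step 3: what it costs.** Exact enumeration of all 31 × 11 outcomes, age-only model, chance that the 95% CI excludes 1:

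| True C8 / C9 cure | Wald | Firth |
|---|---|---|
| 95% / 50% | 68% | 89% |
| 50% / 95% | 19% | 83% |
| 70% / 95% | 0.5% | 26% |
| 75% / 95% | 0.1% | 12% |
| 90% / 50% | 72% | 76% |
| 85% / 60% | 39% | 39% |
| 80% / 50% | 45% | 46% |
| 75% / 50% | 31% | 32% |

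With no age effect, at cure rates of 75% to 90%, Firth excludes 1 in 2.8% to 4.2% of trials and Wald in 1.6% to 2.9%. Both stay below 5%.

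**The case against.** The strongest reply is that little depends on this model. Section 16.1.2 is headed as supportive, section 11 calls all tests exploratory, and sections 8.3 and 8.4 already say that the size of Part 2 limits inferential statistics. The Part 2 primary objective is to evaluate efficacy and safety, not to compare age groups. All of this stands, and it sets the weight of the point.

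A reader might infer that the report would be read as showing no difference between the age groups. The documents do not support that. Cure rates by cohort with exact intervals, subgroup frequencies, forest plots and listings are all planned, so 10/10 would appear beside 15/30. Nor is a Wald test of age planned; what is lost is an informative interval.

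A reader might also infer a general and large loss of power whenever most infants are cured. That goes too far. The trigger is one covariate level with complete response, not a high overall rate. The loss is 0 to 4 points when C8 cures 75% to 90% and C9 50% to 60%. A large loss at 50%/95% needs C8 at 50%, which sits poorly with a dose chosen in Part 1 for an observed cure rate above 70%. When C8 is at 70% to 75% and C9 at 95%, Firth gains but remains weak itself.

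Counting missing as non-response does reduce separation in mITT. It does not protect the per-protocol set, which excludes infants without an end-of-study stool sample and is also reported.

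Finally, changing the estimator alone would not make the listed Part 2 model estimable. With one ODT selected, formulation and active ingredient are constant. Planned dose is constant too, unless it is adapted for C9, in which case it may be collinear with age category. This objection stands in full, and the fix must cover it.

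**Conclusion.** The point holds as a limited defect in a supportive analysis. The SAP commits to Wald intervals for every parameter of a model fitted to about 40 infants and says nothing about separation. If a covariate level is fully cured, the corresponding odds ratio is infinite and its interval cannot exclude 1. For the age contrast alone the chance is about 6% at 75% cure and 38% at 90%; further covariates raise it, and missing outcomes in mITT lower it. The loss is large only when one group is almost fully cured and the gap is wide, and otherwise small. These figures rest on assumed infant cure rates and infection mix, and those for power on an age-only model. The primary Clopper-Pearson estimates by cohort are not affected, so the documents do not support reading this as a threat to the main Part 2 conclusions.

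**What to change.** In SAP section 16.1.2, and for POC-CCA cure in 16.2.1, specify for Part 2 the FIRTH option on the MODEL statement, with profile-likelihood 95% intervals (CLODDS=PL) in place of Wald intervals. In the same sentence, remove from the Part 2 model the terms that are constant or not separately estimable: formulation, active ingredient, and planned dose where it is constant or collinear with age category.

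The cost is two SAS options and a short SAP amendment, with no change to design or data collection. The downside is slight shrinkage of the odds ratios and an estimator that differs from Part 1, unless it is used there as well. This is a cheap improvement, best made before Part 2 data are available so that the method is not chosen after the fact.
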